2.2 Secondary Objectives

2.2.1 To determine impact of PRO monitoring with symptom alerts compared to PRO monitoring without symptom alerts after thoracic surgery on post-operative readmission and mortality rates by analyzing:

1. 30-day post-discharge emergency department visit rate
2. 90-day post-discharge emergency department visit rate
3. 30-day post-discharge readmissions rate
4. 90-day post-discharge readmissions rate
5. 30-day mortality (percentage)
6. 365-day mortality (percentage)
7. Change in 2-year quality of life

2.2.2 To determine feasibility of PRO monitoring after thoracic surgery in regards to monitoring long-term quality of life. Feasibility is defined as $\geq 50\%$ of patients completing all quality of life surveys at baseline and all follow-up time points.

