4.3 Study Details

Participants complete electronic surveys to assess their baseline and post-operative characteristics, symptoms, quality of life, and health outcomes. The study consists of a total number of 9 different surveys.

Figure 2: Survey Frequency and Duration

Survey	Frequency	Completion Time
Pre-operative Symptom Survey	1	5 minutes
Patient Demographics	1	3 minutes
PROMIS Physical Function SF 4a Survey	32	2 minutes
EORTC QLQ-LC13 survey	8	3 minutes
EORTC QLQ-C30 survey	8	8 minutes
Patient Satisfaction survey	7	3 minutes
Readmission Patient Survey	7	2 minutes
Post-operative symptom Daily Survey	15	7 minutes
Post-operative symptom Weekly Survey	11	7 minutes

Enrollment/Baseline Visit

Patients at the multidisciplinary thoracic oncology clinic with plans for thoracic surgery will be approached for enrollment based on inclusion/exclusion criteria described above. An IRB-approved study team member will approach the patient to discuss study procedures, benefits, risks and obtain informed consent prior to any study procedures. The study team member will also teach the patient how to complete the PRO assessment using PRO Core.

At that time, the participant will complete their pre-operative PRO assessment in a private area, which will include PRO surveys as well as demographic questions such as age, sex, and education. PRO survey responses will be reported using the PRO Core database. Paper copies of PRO surveys and source documents will be used if PRO Core system is inaccessible.

For patients who are found to be ineligible during screening or those potentially eligible during screening but found to be ineligible after contact, reasons for ineligibility as well as basic demographics available in the EMR (e.g. race, ethnicity, age, gender, education level if available) will be collected in PRO Core.

For patients who are eligible but refuse enrollment, reasons for refusal, as well as basic demographics available in the EMR (e.g. race, ethnicity, age, gender, education level if available) will also be collected within PRO Core.

Discharge Day (Day 0) Visit:

On the day of discharge (or the next business day in the case of late or weekend discharges), discharge day surveys will be activated in PRO Core by the study staff.

A study team member will call or approach participant in their hospital room before or after discharge to reorient the participant with PRO Core, if needed.

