7.2 Sample Size and Accrual

We originally anticipated 100-150 patients to be enrolled per year. A sample size of 66 in each group will have 80% power to detect a difference in mean EORTC scores of 10.000 assuming that the common standard deviation is 22.900 using two group t-test with a 0.050 one-sided significance level. The target sample size was 140 patients to allow appropriate block randomization in groups of 20. Based on enrolling about 140 patients, we would be powered to detect an effect size of 0.437 (difference in means of 10, common standard deviation of 22.9). Due to slower accrual in context of COVID-19, we anticipate enrollment of 100-140 patients before funding ends. With 100 patients, we will have 80% power to detect an effect size of 0.501 (difference in means of 11.467, common standard deviation of 22.9). Power calculations were performed using SAS version 9.4 (SAS Inc., Cary, NC) using PROC POWER and a two sample means difference test.

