7.3 Data Analysis Plans

7.3.1 Aim 1: Impact of PRO monitoring with symptom alerts, compared to PRO monitoring without alerts, after thoracic surgery on post-operative quality of life.

Impact will be determined by comparing baseline quality of life to quality of life at the following timepoints: Day 14, Day 60, Day 120, Day 180, and Day 365 post-discharge. QOL will be measured by administering European Organisation for Research and Treatment of Cancer's (EORTC) EORTC QLQ-LC13 and EORTC QLQ-C30. These surveys will be scored according to methods described in the EORTC scoring manual: <https://qol.eortc.org/manual/scoring-manual>.

Student's T and/or Wilcoxon rank sum tests will be used to perform bivariable comparisons of EORTC scores at each of the time points (baseline/pre-operative and Day 12, Day 60, Day 120, Day 180, and Day 365 post-operative).

Additionally, a linear mixed effect model will be used to assess the average

change in EORTC scores over time amongst both groups, and the difference in average trajectory between them, after accounting for repeated measures and within- and between- subject variability. Both a random intercept and slope (for time) statement will be used, and an unstructured correlation matrix will be applied. The random intercept and slope will allow us to assess the impact of symptom alerts while allowing for random variation in baseline quality of life and trajectories.

If there are convergence issues, simpler correlation structures may be used (e.g. independent) or the random slope parameter may be dropped. Dropping the random slope parameter will mean we are assuming that there is no/minimal individual variation in trajectory across patients.

7.3.2 Aim 2: Determine feasibility of 3-month post-operative PRO symptom monitoring with alerts.

The proportion of completed symptom surveys (overall and in each arm) at 3-months postoperative will be calculated, as well as the proportion of participants who completed all surveys during that time. Chi-square, Student's T, and Wilcoxon rank sum tests will be used to compare patient demographics, study arm, and surgery characteristics between those who did and did not complete all surveys to attempt to identify predictors of compliance. Multivariable logistic regression may also be used.

Similar methods will be used to assess proportion of symptom alerts that generate a clinician response.

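### The by-visit EORTC tests and the sample-size calculation ignore the baseline score, and the mixed model does not say how baseline enters

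*Combined protocol and SAP*

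**What the plan says.** Section 4.3 has each patient complete baseline surveys at enrolment: "the participant will complete their pre-operative PRO assessment in a private area". Its frequency table gives eight administrations of each EORTC instrument. The visit lists that follow contain seven post-discharge administrations (Days 14, 60, 120, 180, 365, 545 and 730), so the eighth is baseline. The time and events table marks both instruments at baseline, and section 2.2.2 counts the proportion "of patients completing all quality of life surveys at baseline and all follow-up time points".

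Section 7.3.1 (Aim 1) first defines impact as follow-up quality of life compared with baseline. It then says Student's t and/or "Wilcoxon rank sum tests will be used to perform bivariable comparisons of EORTC scores at each of the time points", listed as "baseline/pre-operative and Day 12, Day 60, Day 120, Day 180, and Day 365 post-operative". (The opening sentence of the section has Day 14 where this list has Day 12.) Neither change from baseline nor baseline adjustment is named. The sentence does not say which groups are compared; the Aim 1 title and the two-sample tests imply the two arms.

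A linear mixed model is added, with a random intercept and a random slope for time. Its only words on baseline are that the random effects allow assessment of the alerts "while allowing for random variation in baseline quality of life and trajectories". It lists no fixed effects.

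Section 7.2 states: "A sample size of 66 in each group will have 80% power to detect a difference in mean EORTC scores of 10.000", "using two group t-test with a 0.050 one-sided significance level", with a standard deviation of 22.9. It gives no covariate and no correlation.

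**The concern.** A baseline measure of the outcome is usually among the strongest predictors of the follow-up value, and here it is already collected. A by-visit test that ignores it leaves between-patient variation in the error term. It also departs from the plan's own definition of impact, which is relative to baseline. Listing baseline among the tested time points adds a comparison of randomized groups before any intervention, which says nothing about the effect of alerts.

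Section 7.2 now expects 100–140 patients before funding ends, so recruiting more may not be possible. Precision from data already in hand is then the cheapest remedy.

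The mixed model does not settle the matter. The plan does not say whether baseline is a response or a covariate, whether the arms share a baseline mean, or how time is coded. Nor does it say whether the tests or the model decide Aim 1. The treatment of baseline determines whether the model gains or loses precision against the raw test, and section 7.3.4 reuses the same model for 2-year quality of life.

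**Working it through.** **Inputs.** From sections 7.1 and 7.2: SD 22.9, target difference 10 points, one-sided α 0.05, power 80%, 1:1 allocation. Assumed: the correlation r between baseline and follow-up scores on one scale at one visit. The documents do not give it. I use 0.3, 0.5 and 0.7; it may differ by scale and visit.

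**Plan's own figures.** Noncentral t, n per arm, df = 2n − 2, noncentrality (10/22.9)·√(n/2):
- n = 66: power 0.8025, and 66 is the smallest n reaching 80%. Reproduced.
- n = 50: detectable difference = 2.504 × 22.9 × √(2/50) = 11.47, effect size 0.501. Reproduced. Power for 10 points is 70%.
- n = 70: power for 10 points is 82%, detectable difference 9.67 (effect size 0.422). The plan's figure for 140 patients, "an effect size of 0.437 (difference in means of 10, common standard deviation of 22.9"), is simply 10/22.9.

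All of these are calculations without baseline.

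**Effective SD under three analyses of one visit.**
- Raw score: 22.9
- Baseline-adjusted (ANCOVA): 22.9·√(1 − r²), df = 2n − 3. This is 21.85, 19.83, 16.35 for r = 0.3, 0.5, 0.7.
- Change from baseline, baseline means free by arm: 22.9·√(2(1 − r)), df = 2n − 2. This is 27.10, 22.90, 17.74.

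**Detectable difference at 80% power (points), 100 enrolled.** The attrition rates are illustrative.

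| Analysable per arm | Raw | Adjusted, r = 0.3 / 0.5 / 0.7 |
|---|---|---|
| 50 (none missing) | 11.5 | 10.9 / 9.9 / 8.2 |
| 45 (10% missing) | 12.1 | 11.5 / 10.5 / 8.6 |
| 40 (20% missing) | 12.8 | 12.3 / 11.1 / 9.2 |

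For example, at 50 per arm and r = 0.5: 2.504 × 19.83 × 0.2 = 9.93. The free-baseline change contrast at 50 per arm gives 13.6 / 11.5 / 8.9.

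**Correlation needed to regain 10 points with 100 enrolled.** 0.49 with nothing missing, 0.56 with 10% missing, 0.63 with 20% missing.

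**Power for a true 10-point difference at 50 per arm.** 40,000 simulated trials:

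| r | Raw | Adjusted | Change |
|---|---|---|---|
| 0.3 | 70% | 73% | 57% |
| 0.5 | 70% | 80% | 70% |
| 0.7 | 70% | 91% | 88% |

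The noncentral-t values agree to about one percentage point.

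**Missing baselines.** Complete-case ANCOVA matches the raw test when the loss of patients offsets the variance reduction, that is, when the missing fraction is about r². Solved exactly at 50 per arm, this is 8.9%, 24.6% and 48.3% for r = 0.3, 0.5 and 0.7.

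**The case against.** The strongest reply is that Aim 1 already uses baseline. The random-intercept wording suggests that baseline is the time-0 response, so the efficiency loss belongs to the by-visit tests and not to the whole plan. That stands, and the concern is limited accordingly.

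The reply goes on that the planned model contrasts trajectories over several visits, so the single-visit change figures (13.6 / 11.5 / 8.9) need not apply. Suppose equal correlation r between all visits, a constant effect at all five follow-ups and no missing data. The mean of the five follow-ups minus baseline then has SD 22.9·√(1.2(1 − r)) and detects 10.5 / 8.9 / 6.9 points at 50 per arm, below the raw single-visit 11.5. But this compares a five-visit average with one visit. Under the same assumptions, the raw five-visit mean has SD 22.9·√((1 + 4r)/5) and detects 7.6 / 8.9 / 10.0. The adjusted five-visit mean has SD 22.9·√((1 + 4r)/5 − r²) and detects 6.8 / 6.8 / 6.0. Like for like, the free-baseline contrast still loses below r = 0.5, and adjustment gains at each r shown. A linear-slope contrast is another estimand again, and no figure is given for it here.

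Three further points stand in part:
- Powering on an unadjusted t-test is ordinary practice and conservative relative to ANCOVA.
- The gain rests on an unknown r. Section 1.2 reports that symptoms and function worsen for up to 6 months after surgery, so early correlations could be low. At r = 0.3 the gain is only about half a point.
- With 140 analysable patients the raw test already detects 9.7 points.

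The study is also called a feasibility study. However, quality of life is its first primary objective and the only one with a power calculation.

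**Conclusion.** The concern holds, as an inefficiency and an unspecified choice, not an error. The unadjusted tests are valid and 66 per arm is correct for them. With 100 patients and complete data at the visit, baseline adjustment lowers the detectable difference from 11.5 to 10.9, 9.9 or 8.2 points at r = 0.3, 0.5 or 0.7. It recovers the 10-point target only if r is about 0.49 or more, and r must be higher with attrition. The figures are for one scale at one visit, assume that 22.9 is the SD of raw scores at both baseline and follow-up, and depend on an assumed r. The gaps in the mixed-model specification and in naming the deciding analysis are missing detail. They should be closed because one permissible reading loses precision against the raw test when r is below 0.5. The change should be made; confidence is medium because r is unknown.

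**What to change.** In section 7.3.1, replace the by-visit t/Wilcoxon tests with one of:
1. ANCOVA of the follow-up score on arm, adjusted for the same scale's baseline score; or
2. visit contrasts from the repeated-measures model, with visit as a category and either baseline adjustment or a common baseline mean for both arms.

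Then:
- State which analysis decides Aim 1.
- Report adjusted between-arm differences with confidence intervals.
- Describe baseline by arm instead of testing it.
- Keep the unadjusted test as a sensitivity analysis.
- In section 7.2, give the detectable difference at 100 patients over a stated range of r and attrition.

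The cost is SAP wording and one degree of freedom, with no new data. Complete-case ANCOVA also drops patients without a baseline score; the common-baseline-mean model keeps them.

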Participants will be reminded of the post-discharge survey schedule, helped with any questions they may have, and assisted with completing any due surveys, if needed.

In the case the day of discharge survey is not obtained (e.g late in the day discharges, weekend discharges, and patient unable or unwilling to complete a survey), this will not be considered a protocol deviation.

The study team member activating the discharge day survey will obtain surgical information from Epic, the surgeon or surgery care team member.

Day 0 (Discharge) to Day 14 Post-Discharge

At this time the following procedures will be performed:

- Daily Post-operative symptom survey
- Daily PROMIS Physical Function SF 4a survey

Day 14 (+/- 7 days) Post-Discharge

At this time the following procedures will be performed:

- EORTC QLQ-LC13 survey
- EORTC QLQ-C30 survey
- Patient Satisfaction survey
- Readmission Patient Survey

Day 15 to Day 90 Post Discharge

Weekly symptom monitoring commences. At this time the following procedures will be performed:

- Weekly Post-operative symptom survey
- Weekly PROMIS Physical Function SF 4a survey

Day 60 Post-Discharge (+60 days)

At this time the following procedures will be performed:

- EORTC QLQ-LC13 survey
- EORTC QLQ-C30 survey
- Patient Satisfaction survey
- Readmission Patient Survey

Day 120 Post-Discharge (+60 days)

At this time the following procedures will be performed:

- EORTC QLQ-LC13 survey
- EORTC QLQ-C30 survey
- PROMIS Physical Function SF 4a survey
- Patient Satisfaction survey
- Readmission Patient Survey

Day 180 Post-Discharge (+185 days)

At this time the following procedures will be performed:

- EORTC QLQ-LC13 survey
- EORTC QLQ-C30 survey
- PROMIS Physical Function SF 4a survey
- Patient Satisfaction survey
- Readmission Patient Survey

Day 365 Post-Discharge (+180 days)

At this time the following procedures will be performed:

- EORTC QLQ-LC13 survey
- EORTC QLQ-C30 survey
- PROMIS Physical Function SF 4a survey
- Patient Satisfaction survey

Day 545 Post-Discharge (+185 days)

At this time the following procedures will be performed:

- EORTC QLQ-LC13 survey
- EORTC QLQ-C30 survey
- PROMIS Physical Function SF 4a survey
- Patient Satisfaction survey

Day 730 Post-Discharge (+185 days)

At this time the following procedures will be performed:

- EORTC QLQ-LC13 survey
- EORTC QLQ-C30 survey
- PROMIS Physical Function SF 4a survey
- Patient Satisfaction survey

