7.0 STATISTICAL CONSIDERATIONS

7.1 Study Design

This is a single center, randomized feasibility study. A total of 140 patients undergoing thoracic surgery will be prospectively enrolled and randomized in a 1:1 ratio. A random block method with blocks of 20 will be utilized to randomize participants to one of two arms to complete PRO (patient reported outcome) symptom monitoring. The two arms are 1) active symptom monitoring and 2) passive symptom monitoring. The participants randomized to active symptom monitoring will have alerts sent to their clinicians when their PRO symptom scores exceed baselines scores by 2 points or more, or when 'severe' or 'very severe' symptoms are reported. Participants randomized to the passive PRO monitoring arm will complete the same PROs as participants in the active monitoring arm, but will not have alerts sent to their clinician. All participants will be administered survey instruments to further assess quality of life including: EORTC QLQ30, EORTC LC13, PROMIS Physical Function SF 4a survey SF 4a. Additionally, in order to assess the feasibility of the PRO monitoring system, all participants will be asked to complete a Patient Satisfaction survey. In addition, a subset of 40 participants and 40 caregivers will be chosen to complete a semi-structured interview, if willing, to assess patient satisfaction with symptom monitoring experience. The subset will be made up of a range of post-operative experiences and will be a fair representation of study population, including both

study arms. Participants will be chosen by principal investigator and eligible to participate in interview after 14 days of discharge

The primary objectives are to determine 1) impact of PRO monitoring with symptom alerts compared to PRO monitoring without symptom alerts after thoracic surgery on post-operative quality of life 2) feasibility of 3-month post-operative PRO symptom monitoring after thoracic surgery symptom monitoring eliciting a clinician response 3) barriers/facilitators of PRO monitoring after thoracic surgery through semi-structured interviews of patients.

Secondary objectives include: 1) determining impact of PRO monitoring with symptom alerts compared to PRO monitoring without symptom alerts after thoracic surgery on post-operative readmission and mortality rates 2) determining feasibility of PRO monitoring after thoracic surgery in regards to monitoring quality of life.

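### Aim 1's quality-of-life comparison relies on returned EORTC forms alone, so it is biased if non-return differs by arm, and the collected symptom and PROMIS scores that would reduce this go unused

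*Combined protocol and SAP*

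**What the plan says.** Section 7.3.1 plans two analyses of EORTC scores. First, t and/or Wilcoxon "tests will be used to perform bivariable comparisons of EORTC scores at each of the time points", from baseline to Day 365. (That list gives Day 12 where the schedule has Day 14; the two need reconciling.) Second, "a linear mixed effect model will be used to assess the average" change and the difference in trajectory between arms, with a random intercept and slope. The model is introduced as an addition, and neither analysis is called primary. Aim 1 has no missing-data method, missingness assumption, sensitivity analysis or rule for deaths. The only loss-to-follow-up rule and the only intent-to-treat statement belong to Sub-Aim 1 (7.3.4).

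Section 7.2 allows nothing for non-return; the step from 132 to 140 is for block size: "The target sample size was 140 patients to allow appropriate block randomization in groups of 20". Section 2.2.2 counts long-term monitoring as feasible if at least half "of patients completing all quality of life surveys at baseline and all follow-up time points". Section 4.3 schedules symptom surveys daily to Day 14 and weekly to Day 90, alongside PROMIS ("Daily PROMIS Physical Function SF 4a survey", then weekly). No Aim 1 analysis uses these scores. Sub-Aim 2 (7.3.5) looks for predictors of completing the QOL forms but does not carry them into Aim 1.

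**The concern.** Returning a form is behaviour after randomisation, and the intervention may alter it. Both arms are sent the same surveys, but only in the active arm can a bad report bring a clinician response. Symptomatic passive-arm patients might stop responding while similar active-arm patients continue. The remaining passive-arm patients would then look healthier than those randomised, and a benefit of alerts would be understated. The opposite pattern would exaggerate a benefit. This would be bias in a primary objective, which more patients would not cure. Meanwhile the trial collects up to 26 symptom and 26 PROMIS reports per patient over Days 0-90 that probably predict both quality of life and non-return.

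**Working it through.** **Plan's own figure.** Section 7.2: "A sample size of 66 in each group will have 80% power to detect a difference in mean EORTC scores of 10.000", where the "common standard deviation is 22.900 using two group t-test with a 0.050 one-sided significance level". With the noncentral t distribution, 65 per arm gives 79.7% power and 66 gives 80.3%, so 66 reproduces. The 100-patient figure (50 per arm, difference 11.467) gives 80.0% and also reproduces. Both assume that every patient has a score. At 70 per arm and a difference of 10, one-sided power at a visit is 82.3% with full return, 74.3% at 80% return (56 per arm) and 69.2% at 70% (49 per arm).

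**Unused reports.** Section 4.3, Figure 2: 15 daily + 11 weekly = 26 symptom surveys. The 32 PROMIS surveys are the same 26 plus baseline and Days 120, 180, 365, 545 and 730 (26 + 1 + 5 = 32).

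**Bias of a per-visit test.** From the plan: SD 22.9 and a target of 10. Assumed: an earlier symptom/PROMIS z-score x, correlated r = 0.6 to 0.8 with the EORTC score (higher is better); log-odds of return rising linearly in x with slope s; return 78% active and 66% or 70% passive; no true difference. Then

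bias = 22.9 × r × (m_active − m_passive),

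where m is the mean of x among patients who return the form, found by numerical integration:

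| Return | m at s = 0.7 | m at s = 1 |
|---|---|---|
| 78% | 0.1423 | 0.1893 |
| 70% | 0.1915 | 0.2528 |
| 66% | 0.2160 | 0.2845 |

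If s = 0, m = 0. Also 22.9 × 0.6 = 13.74 and 22.9 × 0.8 = 18.32.

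- Same slope (1) in both arms: from 13.74 × (0.1893 − 0.2528) = -0.9 to 18.32 × (0.1893 − 0.2845) = -1.7.
- Selection in the passive arm only (active s = 0): from 13.74 × (0 − 0.1915) = -2.6 to 18.32 × (0 − 0.2845) = -5.2.
- Same slope and same return rate: m is equal in both arms, so the bias is 0.
- Return rates swapped, same slope 1: +0.9 to +1.7.

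A large simulation of the same set-up agreed to within about 0.1 point.

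**What the mixed model recovers.** This was simulated over six visits with a true difference of 10, between-visit correlation 0.5, auxiliary correlation 0.7 and slope 1. A maximum-likelihood repeated-measures model with unstructured means and covariance stands in for the planned model. Bias:

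| Return active/passive | Visit | Returned forms only | EORTC-only model | With auxiliaries |
|---|---|---|---|---|
| 80%/70% | Day 14 | -1.2 | -0.9 | 0.0 |
| 80%/70% | Day 60 | -1.4 | -1.0 | -0.1 |
| 80%/60% | Day 14 | -2.4 | -1.6 | 0.0 |
| 80%/60% | Day 60 | -2.5 | -1.8 | 0.0 |
| 80%/60% | Days 120-365 | about -2.5 | about -1.8 | about -1.7 |

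The EORTC-only model removes roughly a quarter to a third of the bias. The auxiliaries remove nearly all of it at Days 14 and 60, where they are assumed to drive return, and little afterwards. Symptom surveys end at Day 90, and from Day 120 PROMIS falls due with the EORTC form.

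**Limits of the auxiliaries.** In the 78% versus 66-70% set-up, if half of the non-returners also lack x, imputation leaves about -0.3 to -0.6 (same slope 1) or -1.1 to -2.1 (passive-only selection). If return depends on the unseen EORTC score itself (80%/60%, slope 1), bias is -3.6 on returned forms and still -1.8 with baseline and auxiliary scores.

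**The case against.** The strongest reply is that nothing in the documents shows that bias will occur. They give no return rates and no evidence that return differs by arm. Sicker patients responding less often is not enough: if that happens equally in both arms, the difference is about unbiased. This stands, and the point is conditional for that reason.

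A reader might take the 50% feasibility threshold as an expectation that half the forms will be missing at a visit. It is a success criterion, and it covers all eight EORTC administrations. If exactly half of patients completed all eight, independent returns would imply 1 − 0.5^(1/8) = 8% non-return per visit. The figure would be 0.5/8 = 6% if each non-completer missed one form, and 50% if they missed all. The 22-34% used above lies inside that range but is not implied by it. The late windows in section 4.3 (for example +60 days at Days 60 and 120, +185 at Day 180) should also lower non-return.

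A reader might also infer that a true 10-point benefit would typically shrink to 5-7, or that imputation removes the bias altogether. The first needs strong selection in one arm and almost none in the other. The second needs the auxiliary score to drive non-return and to be observed. All surveys run through the same PRO Core system, so a patient who stops responding may leave neither.

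Finally, the planned mixed model is valid if return depends only on arm and observed EORTC scores. That narrows the gap without closing it, and the plan does not say that the model carries the conclusion.

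**Conclusion.** The point holds as a conditional weakness. Aim 1's per-visit tests use returned forms only, its mixed model uses EORTC scores only, and relevant scores already collected are left out. If the rate or the health-dependence of non-return differs by arm, the comparison is biased with unknown sign. Under the assumed return rates this is about 1 to 2 points with equal selection strength, and about 3 to 5 only with strong selection confined largely to one arm, against a design difference of 10. The mixed model would take off roughly a quarter to a third. All of these sizes rest on assumed return rates, slopes and correlations. Correction from the auxiliary scores is well supported at Days 14 and 60, two of the five post-baseline Aim 1 visits. The change is worth making because it is cheap and needs no new data.

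**What to change.** In 7.3.1:

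1. Name the repeated-measures mixed model as the main Aim 1 analysis, state its missingness assumption, and make the per-visit tests descriptive.
2. Add multiple imputation, separately by arm, for patients alive at each visit. Use baseline and other EORTC scores, a small set of summary symptom and PROMIS scores (means over Days 0-14 and Days 15-90) and chart-abstracted readmission. Refit the mixed model and the per-visit mean differences on the imputed data, and show the observed-forms results beside them.
3. Add a delta-adjusted sensitivity analysis that shifts imputed scores by a range of amounts, separately by arm. It is needed because the auxiliaries help little at Days 120-365 and not at all for patients who stop every survey.

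The cost is plan wording and modest programming. With 50-70 patients per arm the imputation model must stay small, which is why summary scores are preferable to the individual daily and weekly reports.
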